2.8 Safety analyses

All safety analyses will be based on the safety set. All listings and tables will be presented for each cohort.

The assessment of safety will be based mainly on the frequency of adverse events and on the number of laboratory values that fall outside of pre-determined ranges. Other safety data (e.g., ECG, vital signs) will be considered as appropriate. All safety data will be listed.

2.8.1 Adverse events (AEs)

AE summaries will include all AEs occurring during on treatment period (**treatment-emergent AEs**). All AEs collected in the AE (e)CRF page will be listed along with the information collected on those AEs e.g. AE relationship to study drug, AE outcome etc. AEs with start date outside of on-treatment period will be flagged in the listings.

AEs will be summarized by number and percentage of patients having at least one AE, having at least one AE in each primary system organ class (SOC) and for each preferred term (PT) using MedDRA coding. A patient with multiple occurrences of an AE will be counted only once in the respective AE category. A patient with multiple CTCAE grades for the same preferred term will be summarized under the maximum CTCAE grade recorded for the event. AE with missing CTCAE grade will be included in the 'All grades' column of the summary tables.

In AE summaries, the primary system organ class will be presented alphabetically and the preferred terms will be sorted within primary SOC in descending frequency. The sort order for the preferred term will be based on their frequency in the investigational drug .

The following adverse event summaries will be produced by cohort: overview of adverse events and deaths, AEs by SOC and PT, summarized by relationship, seriousness, leading to treatment discontinuation, leading to dose interruption/adjustment, requiring additional therapy and leading to fatal outcome. In addition, a summary of serious adverse events with number of occurrences will be produced (an occurrence is defined as >1 day between start and prior end date of record of same preferred term).

2.8.1.1 Adverse events of special interest / grouping of AEs

Data analysis of AESIs

An adverse event of special interest is a grouping of adverse events that are of scientific and medical concern specific to compound BYL719. These groupings are defined using MedDRA terms, SMQs (standardized MedDRA queries), HGLTs (high level group terms), HLT (high level terms) and PTs (preferred terms). Customized SMQs (Novartis MedDRA queries, NMQ) may also be used. A NMQ is a customized group of search terms which defines a medical concept for which there is no official SMQ available or the available SMQ does not completely fit the need. It may include a combination of single terms and/or an existing SMQ, narrow or broad. For each specified AESI, number and percentage of patients with at least one event of the AESI occurring during on treatment period will be summarized.

A Case Retrieval Sheet (CRS; an Excel file) with the exact composition of the adverse events groupings is to be used to map reported adverse events to the AESIs groupings (termed Specific Event Categories (SECs) in the CRS). This file may be updated (i.e. it is a living document) based on review of accumulating trial data. The latest version of the CRS document available at the time of the analyses will be used.

Summaries of these AESIs will be provided by cohort (specifying grade, SAE, relationship, leading to treatment discontinuation, leading to dose adjustment/interruption, hospitalization, death etc.). If sufficient number of events occurred, analysis of time to first occurrence will be applied.

Depending on the observed number of events, the time to first occurrence of any CTC grade > 2 AESI may be summarized using Kaplan-Meier methods for specific groupings.

Median time to onset and 95% CI will be summarized. Ascending Kaplan-Meier lots will be generated.

A listing of all grouping levels down to the MedDRA preferred terms used to define each AESI will be generated.

2.8.2 Deaths

Separate summaries for on-treatment and all deaths will be produced by cohort, system organ class and preferred term.

All deaths will be listed, post treatment deaths will be flagged. A separate listing of deaths prior to starting treatment will be provided for all screened patients.

2.8.3 Laboratory data

On analyzing laboratory, data from all sources (central and local laboratories) will be combined. The summaries will include all assessments available for the lab parameter collected no later than 30 days after the last study treatment administration date (see [Section 2.1.1](#)).

The following summaries will be produced for hematology, biochemistry and urinary laboratory data (by laboratory parameter and treatment):

- Worst post-baseline CTC grade (regardless of the baseline status). Each patient will be counted only for the worst grade observed post-baseline.
- Shift tables using CTC grades to compare baseline to the worst on-treatment value.
- For laboratory tests where CTC grades are not defined, shift tables using the low/normal/high/(low and high) classification to compare baseline to the worst on-treatment value.
- Trends of lab parameter values over time (baseline and selected on-treatment timepoints) might be displayed via boxplots based on time windows and corresponding tables displaying the statistics used for the box plots by the selected time points.
- In addition, HbA1c, fasting glucose and fasting C-peptide data will be summarized in tables by time point and treatment. Summary statistics include number of patients with available data, mean, standard deviation, median, minimum and maximum. Figures of mean

HbA1c/glucose/C-peptide levels with two-sided 95% confidence intervals over time by cohort may also be produced to view the trends over time.

The following listings will be produced for the laboratory data:

- Listings of all laboratory data, with CTC grades and classification relative to the laboratory normal range. Lab data collected during the post-treatment period will be flagged.
- Listing of all CTC grade 3 or 4 laboratory toxicities

Liver function parameters

Liver function parameters of interest are total bilirubin (TBL), ALT, AST and alkaline phosphatase (ALP). The number (%) of patients with worst post-baseline values as per Novartis Liver Toxicity guidelines will be summarized:

The following summaries will be produced:

- ALT or AST > 3xULN
- ALT or AST > 5xULN
- ALT or AST > 8xULN
- ALT or AST > 10xULN
- ALT or AST > 20xULN
- TBL > 2xULN
- TBL > 3xULN
- ALT or AST > 3xULN & TBL > 2xULN
- ALT or AST > 3xULN & TBL > 2xULN & ALP < 2xULN (potential Hy's law)

Potential Hy's Law events are defined as those patients with concurrent occurrence of AST or ALT > 3xULN and TBL > 2xULN and ALP < 2xULN in the same assessment sample during the on-treatment period.

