7.2.2.5 Laboratory evaluations

Clinical laboratory analyses (hematology, fasting biochemistry (full or partial), fasting lipase, fasting amylase, fasting lipid panel/glucose/c-peptide, HbA1_C, coagulation, pregnancy test and urinalysis) are to be performed by the central laboratory. In case of urgent safety management of hyperglycemia, fasting or random blood glucose assessment may be done locally according to the schedule of assessments and collection plan outlined respectively in Table 7-1 and Table 7-5 for the Core Phase.

Note: as hyperglycemia typically occurs within the first weeks of treatment, blood glucose at Day 8 and Day 15 of Cycle 1 should be performed both locally and centrally for rapid availability for safety evaluation and dose adjustments.

Unscheduled local laboratory assessments may be performed if medically indicated to assess a (potential) adverse event or when the treating physician cannot wait for central laboratory results for decision making (e.g. dose modifications) during the Core Phase. In this particular situation, if possible, the blood sample obtained at the same time point should be submitted to the central laboratory for analysis in parallel with local analysis. During the Extension Phase, all labs will be sent to local laboratory for testing.

The results of the local laboratory during the Core Phase will be recorded in the eCRF if any of the following criteria are met:

- A treatment decision was made based on the local results, or
- Local lab results document an adverse event not reported by the central lab, or
- Local lab results document an adverse event severity is worse than the one reported by the central lab, or
- There are no concomitant central results available

At any time during the study, abnormal laboratory parameters which are clinically relevant and require an action to be taken with study treatment (e.g. require dose modification and/or interruption of study treatment, lead to clinical symptoms or signs, or require therapeutic intervention), whether specifically requested in the protocol or not, will be recorded on the AE eCRF page. Laboratory data will be summarized using the Common Terminology Criteria for Adverse events (CTCAE) version 4.03. Additional analyses are left to the discretion of the investigator.

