from day of patient’s informed consent to the day before first administration of study treatment.
- ***on-treatment period:***
from date of first administration of study treatment to 30 days after date of last actual administration of any study treatment (including start and stop date).
- ***post-treatment period:***
starting at day 31 after last administration of study treatment.

Safety summaries (tables, figures) include only data from the on-treatment period with the exception of baseline data which will also be summarized where appropriate (e.g. change from baseline summaries). In addition, a separate summary for death including on treatment and post treatment deaths will be provided. In particular, summary tables for adverse events (AEs) will summarize only on-treatment events, with a start date during the on-treatment period (***treatment-emergent*** AEs).

However, all safety data (including those from the post-treatment period) will be listed and those collected during the pre-treatment and post-treatment period will be flagged.

Windows for multiple assessments

In order to summarize laboratory parameters, vital sign and other data collected over time (including unscheduled visits), the assessments will be time slotted. The following general rule will be applied in creating the assessment windows: If more than one assessment is done within the same time window, the assessment performed closest to the target date will be used. If 2 assessments within a time window are equidistant from the target date, then the earlier of the 2 assessments will be used. If multiple assessments on the same date then the worst case will be used. Data from all assessments (scheduled and unscheduled), including multiple assessments, will be listed.

Time windows for laboratory assessments

Assessment	Target day of assessment	Time Interval
Baseline		\leq Day 1
Cycle 1 Day 8	8	Day 2 to day 11
Cycle 1 Day 15	15	Day 12 to day 21
Cycle 2 Day 1	29	Day 22 to day 42
Cycle 3 Day 1	57	Day 43 to day 63
Cycle 3 Day 15	71	Day 64 to day 77
Cycle 4 Day 1	85	Day 78 to day 98
Cycle k Day 1 ($k \geq 5$)	$d = (k-1) * 28 + 1$	Day $d-14$ to day $d+13$
End of Treatment		Assessment taken at the end of treatment visit

Last contact date

The last contact date will be derived for patients not known to have died at the analysis cut-off using the last complete date among the following:

Table 2-1 Last contact date data sources

Source data	Conditions
Date of Enrollment	No condition

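### Glucose means by visit pool selectively recorded local results with central ones and keep the worst same-day value, which pushes the C1D8 and C1D15 means upward by a probably small amount

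*SAP*

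**What the plan says.** Four provisions act together.

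- **Entry of local results (Protocol 7.2.2.5).** A local result from the Core Phase goes into the eCRF if any one of four conditions is met. Three depend on what the result was or led to. It may have driven a decision about treatment, or shown an adverse event that was missed centrally. The third such condition reads: "Local lab results document an adverse event severity is worse than the one reported by the central lab". The last of the four, absence of a matching central result, does not depend on the value.
- **Planned pairs (Protocol 7.2.2.5).** Because hyperglycemia is expected in the first weeks, "blood glucose at Day 8 and Day 15 of Cycle 1 should be performed both locally and centrally".
- **Pooling (SAP Amendment 4, 2.8.3).** "On analyzing laboratory, data from all sources (central and local laboratories) will be combined". No order of preference between the sources is given.
- **Choice of value (SAP Amendment 4, 2.1.1, windows for multiple assessments).** Within a time window the assessment closest to the target day is used. For ties on the same day the rule is: "If multiple assessments on the same date then the worst case will be used".

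The outputs concerned are also in SAP 2.8.3. The table is a commitment: "In addition, HbA1c, fasting glucose and fasting C-peptide data will be summarized in tables by time point and treatment", with mean, SD, median, minimum and maximum. The figure is optional: mean "levels with two-sided 95% confidence intervals over time by cohort may also be produced to view the trends over time". Boxplots over time are optional too. The extension-phase SAP refers back to Amendment 4 for the main analyses and changes none of this.

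**The concern.** Keeping the worst value is a sensible convention when the output is a worst grade or a shift table. A mean by visit is meant to estimate the typical level at that visit, and a rule that picks one of two readings because it is worse does not do that. The rule also acts unevenly over time. Pairs are planned only at C1D8 and C1D15, while most other visits rest on a single central value. A reader of the glucose profile could therefore see part of an early rise that comes from the selection rule and not from the drug. Hyperglycemia is a leading toxicity of alpelisib, so these two visits are likely to be looked at.

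**Working it through.** **No figure to reproduce.** The plan gives no expected glucose level, no local-central disagreement and no expected share of paired results. What follows is direction from the rules and size from stated assumptions.

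**Direction.** For a patient with both results on the same date, the value used is max(central, local) if worst means highest. This is never below the central value, so the mean can move only upward relative to central-only data.

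**Inputs for size.**

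- From the documents: n = 112 per cohort (SAP 3.1); glucose grade boundaries 160, 250 and 500 mg/dL (Protocol Table 6-3).
- Assumed: true mean 150 mg/dL; between-patient SD 35 mg/dL; within-laboratory CV 3%, 5% or 8%, independent between laboratories; upper limit of normal 105 mg/dL; a same-date pair in every patient.

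**Standard error of a cohort mean.** 35/√112 = 35/10.58 = 3.3 mg/dL.

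**Upper bound: every local value entered.** For two readings with independent error SD s, E[max] − mean = s/√π, with s = CV × 150.

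- CV 3%: 4.5/1.772 = +2.5 mg/dL
- CV 5%: 7.5/1.772 = +4.2 mg/dL
- CV 8%: 12/1.772 = +6.8 mg/dL

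This is too generous. Protocol 7.2.2.5 does not admit a local value merely because it is numerically higher. It must show an adverse event that central does not, show a worse severity, have driven a decision, or stand alone.

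**Applying the entry conditions (simulation, same assumptions).**

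| Local value entered when | CV 3% | CV 5% | CV 8% |
|---|---|---|---|
| its grade is higher than central | +0.3 | +0.9 | +2.2 |
| its grade is higher, or it exceeds 160 mg/dL | +1.4 | +2.5 | +4.4 |
| always (upper bound) | +2.5 | +4.2 | +6.8 |

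Entries are mg/dL. The second row uses any value above 160 as a rough stand-in for results that led to a treatment decision. In standard errors, the first two rows run from 0.3/3.3 = 0.1 to 4.4/3.3 = 1.3. Moving the assumed upper limit of normal between 100 and 110 changes the entries by at most about 0.1 mg/dL.

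**Fewer pairs.** The shift scales with the share of patients who have a pair. If half do, the range is 0.15 to 2.2 mg/dL.

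**Larger disagreement.** A second simulation assumed mean 140, between-patient SD 45 and error SD 5 to 20 mg/dL per reading, to cover handling and timing as well as assay error. Under the second-row entry rule it gave +1.1 to +7.6 mg/dL. Coverage of a nominal 95% interval fell from about 94% at error SD 5 to 67% at error SD 20. The result is sensitive to an input the documents do not supply.

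**The case against.** Several counter-arguments have force.

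- **Worst is not defined for glucose.** SAP 5.3 summarises tests graded in both directions separately, so the SAP recognises two directions but does not say which one governs here. Highest is the natural reading for this drug, but it remains a reading.
- **Not every entered local value is high.** The condition of no central result is neutral. A treatment decision can also rest on a resolved value, since Table 6-3 ties re-starting alpelisib to glucose recovery.
- **Fewer fasting pairs than planned pairs.** The table is for fasting glucose, but Protocol 7.2.2.5.3 allows random testing from C1D8. Where either reading is random there is no fasting pair.
- **Little rests on these means.** The study is non-comparative and no hypothesis uses them. Hyperglycemia is also described by worst grade, shift tables, adverse event and special-interest summaries, and possibly time to first event.

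All four stand, and they limit the size and importance of the point. They do not remove it: no provision exempts the means from pooling or from the same-date rule. For duplicate ECGs, SAP 2.8.4.1 averages, so a neutral rule is already used elsewhere in the plan.

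A reader might infer three stronger things that the documents do not support:

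- **Intervals shifted by 0.8 to 2 standard errors.** That is the upper bound, and it requires entry of every higher local value.
- **An inflated rise from baseline as a certainty.** Protocol 7.2.2.5 also permits local tests for inclusion criteria, and the baseline slot falls under the same window rules, so some offset is possible.
- **The same bias in HbA1c and C-peptide.** Protocol 7.2.2.5.3 assigns both to the central laboratory and no pairs are planned.

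**Conclusion.** The point holds as a matter of rule: result-dependent entry, pooling and worst-of-day selection together push the fasting glucose means at C1D8 and C1D15 upward, provided worst means highest. The size cannot be derived from the documents. Under the main assumptions it is about +0.3 to +4.4 mg/dL (0.1 to 1.3 standard errors at n = 112), with +2.5 to +6.8 mg/dL as an upper bound. It shrinks with fewer fasting pairs and grows if the two laboratories disagree by more than assumed. At other visits, where no pairs are planned, it should be smaller and is less certain. The tables of means are definite; the confidence intervals are affected only if the optional figures are produced. The primary endpoint, other efficacy results and grade-based safety tables are untouched. This is a cheap correction to descriptive safety output, not a threat to the study's conclusions.

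**What to change.** Add one sentence to SAP 2.8.3: for glucose means, boxplots and mean figures by time point, when central and local results exist on the same date the central result is used, and a local result is used only if there is no central result on that date.

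Leave the closest-to-target window rule as it is. Preferring central across the whole window would override it: the C1D15 window runs from day 12 to day 21, so a central value on day 21 could displace a local value on day 15. On dates without a central result, the fourth entry condition lets in any local value whatever its level, so selection by entry does not arise there.

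Keep pooled, worst-value data for worst-grade, shift and notable-value tables, so that no safety signal is lost.

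The cost is the sentence and a source filter in programming. Little information should go missing from the means, because Protocol 7.2.2.5 asks that samples tested locally in the Core Phase also be sent for central analysis.

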If no measurable disease is present, then at least one predominantly lytic bone lesion must be present (Patients with no measurable disease and only one predominantly lytic bone lesion that has been previously irradiated are eligible if there is documented evidence of disease progression of the bone lesion after irradiation).

- 9. Patient has adequate bone marrow and coagulation function as shown by the following laboratory values:
 - Absolute Neutrophil Count (ANC) $\geq 1.5 \times 10^9/L$
 - Platelets $\geq 100 \times 10^9/L$ (For patients with lesions involving the bone marrow, platelet count $\geq 75 \times 10^9/L$ may be acceptable)
 - Hemoglobin $\geq 9.0 \text{ g/dL}$
 - INR \leq 1.5 (INR \leq 2.0 will be allowed for those patients treated with vitamin K antagonist)
- 10. Patient has adequate liver function as shown by:
 - In absence of liver metastases, serum aspartate aminotransferase (AST) and alanine aminotransferase (ALT) \leq 2.5 x ULN or \leq 5 x upper limit of normal (ULN) if hepatic metastases are present,
 - Total serum bilirubin <2 x ULN (any elevated bilirubin should be asymptomatic at enrollment) except for patients with Gilbert's syndrome who may only be included if the total bilirubin is $< 3.0 \times$ ULN or direct bilirubin $< 1.5 \times$ ULN
- 11. Patient has adequate renal function:
 - Serum creatinine ≤ 1.5 x ULN or creatinine clearance ≥ 35 ml/min using Cockcroft-Fault formula

- 12. Patient has fasting plasma glucose (FPG) ≤140 mg/dL (7.7 mmol/L) and glycosylated hemoglobin (HbA1c) ≤ 6.4% (both criteria have to be met)

 *For patients with FPG ≥ 100 mg/dL and/or HbA1c ≥5.7% (i.e. threshold for pre-diabetes) at screening, recommend lifestyle changes according to ADA guidelines, i.e. dietary advice (e.g. small frequent meals, low carbohydrate content, high fiber, balancing carbohydrate intake over the course of the day, three small meals and 2 small snacks rather than one large meal) and exercise. A consultation with a diabetologist is highly recommended.
- 13. Patient has potassium, magnesium and calcium (corrected for albumin), within normal limits (either by central or local lab), or ≤ Grade 1 severity according to NCI-CTCAE v4.03 if judged clinically not significant by the investigator, or correctable with supplements before entry of study; re-screen is allowed.
- 14. Fasting serum amylase $\leq 2 \times ULN$.
- 15. Fasting serum lipase \leq ULN.

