14.4 Appendix 4 – Liver event and Laboratory trigger Definitions and Follow-up Requirements

Table 14-5 Liver event and laboratory trigger definitions

	Definition/ threshold
Liver laboratory triggers If ALT, AST and total bilirubin normal at baseline:	· ALT or AST > 5 × ULN · ALP > 2 × ULN (in the absence of known bone pathology) · Total bilirubin > 3 × ULN (in the absence of known Gilbert syndrome) · ALT or AST > 3 × ULN and INR > 1.5 · Potential Hy's Law cases (defined as ALT or AST > 3 × ULN and Total bilirubin > 2 × ULN [mainly conjugated fraction] without notable increase in ALP to > 2 × ULN) · Any clinical event of jaundice (or equivalent term) · ALT or AST > 3 × ULN accompanied by (general) malaise, fatigue, abdominal pain, nausea, or vomiting, or rash with eosinophilia · Any adverse event potentially indicative of a liver toxicity*
If ALT or AST abnormal at baseline:	· ALT or AST > 2x baseline or > 300 U/L (whichever occurs first)

^{*}These events cover the following: hepatic failure, fibrosis and cirrhosis, and other liver damage-related conditions; non-infectious hepatitis; benign, malignant and unspecified liver neoplasms ULN: upper limit of normal

Table 14-6 Follow-up requirements for liver laboratory triggers with liver symptoms

ALT	TBL	Liver Symptoms	Action
ALT increase without b	ALT increase without bilirubin increase:		
If normal at baseline: ALT > 3 x ULN	Normal For participants with	None	· No change to study treatment
If elevated at baseline: ALT > 2 x baseline	Gilbert's syndrome: No change in baseline TBL		· Measure ALT, AST, ALP, GGT, TBIL, INR, albumin, CK, and GLDH in 48-72 hours.
or > 300 U/L (whichever occurs first)			· Follow- up for symptoms.
If normal at baseline: ALT > 5 x ULN for more than two weeks	Normal For participants with Gilbert's syndrome: No	None	· Interrupt study drug · Measure ALT, AST, ALP, GGT, TBIL, INR,
If elevated at baseline: ALT > 3 x baseline or > 300 U/L (whichever occurs	change in baseline TBL		albumin, CK, and GLDH in 48-72 hours. · Follow- up for symptoms.

ALT	TBL	Liver Symptoms	Action
first) for more than two weeks			Initiate close monitoring and workup
If normal at baseline: ALT > 8 x ULN	Normal	None	for competing etiologies.
ALT increase with bilir	ubin increase:		 Study drug can be restarted only if
If normal at baseline: ALT > 3 x ULN	TBL > 2 x ULN (or INR > 1.5)	None	another etiology is identified and liver

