If elevated at baseline: ALT > 2 x baseline or > 300 U/L (whichever occurs first)	For participants with Gilbert's syndrome: Doubling of direct bilirubin		enzymes return to baseline.
If normal at baseline: ALT > 3 x ULN	Normal or elevated	Severe fatigue, nausea, vomiting, right	
If elevated at baseline: ALT > 2 x baseline or > 300 U/L (whichever occurs first)		upper quadrant pain	

Table 14-7 Follow-up requirements for liver laboratory triggers

Criteria	Actions required	Follow- up monitoring
Total Bilirubin (isolated)		
>1.5 – 3.0 ULN	Maintain treatment Repeat LFTs within 48-72 hours	Monitor LFTs weekly until resolution ^c to ≤ Grade 1 or to baseline
> 3 - 10 × ULN (in the absence of known Gilbert syndrome)	Interrupt treatment Repeat LFT within 48-72 hours Hospitalize if clinically appropriate Establish causality Record the AE and contributing factors (e.g. conmeds, med hx, lab) in the appropriate CRF	Monitor LFTs weekly until resolution ^c to ≤ Grade 1 or to baseline (ALT, AST, total bilirubin, Alb, PT/INR, ALP and GGT) Test for hemolysis (e.g. reticulocytes, haptoglobin, unconjugated [indirect] bilirubin)
> 10 x ULN	Discontinue the study treatment immediately Hospitalize the participant Establish causality Record the AE and contributing factors(e.g. conmeds, med hx, lab) in the appropriate CRF	ALT, AST, total bilirubin, Alb, PT/INR, ALP and GGT until resolution ^c (frequency at investigator discretion)

Criteria	Actions required	Follow- up monitoring
Any AE potentially indicative of a liver toxicity*	Consider study treatment interruption or discontinuation Hospitalization if clinically appropriate Establish causality Record the AE and contributing factors (e.g., conmeds, med hx, lab) in the appropriate CRF	Investigator discretion

^aElevated ALT/AST > 3 × ULN and TBL > 2 × ULN but without notable increase in ALP to > 2 × ULN ^b(General) malaise, fatigue, abdominal pain, nausea, or vomiting, or rash with eosinophilia ^cResolution is defined as an outcome of one of the following: (1) return to baseline values, (2) stable values at three subsequent monitoring visits at least 2 weeks apart, (3) remain at elevated level after a maximum of 6 months, (4) liver transplantation, and (5) death.

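### The combined liver row and the potential Hy's law row in SAP 2.8.3 do not separate patients who already met half the criterion at entry

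*SAP*

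**What the plan says.** **The two rows.** SAP 2.8.3 lists liver thresholds to be counted on worst post-baseline values. One row combines ALT or AST above 3xULN with TBL above 2xULN. The next adds an ALP condition: "ALT or AST > 3xULN & TBL > 2xULN & ALP < 2xULN (potential Hy's law". The event is then defined as "concurrent occurrence of AST or ALT > 3xULN and TBL > 2xULN and ALP < 2xULN in the same assessment sample" during the on-treatment period. All limits are multiples of ULN, and none refers to the patient's own baseline.

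**Who may enter.** Protocol 5.2, criterion 10, limits ALT and AST to 2.5xULN, or to 5 times the "upper limit of normal (ULN) if hepatic metastases are present". TBL must be below 2xULN, "except for patients with Gilbert's syndrome who may only be included if the total bilirubin is" below 3.0xULN, or direct bilirubin below 1.5xULN.

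**How the protocol treats raised baselines.**
- Table 14-5 places its potential Hy's law trigger under the heading "If ALT, AST and total bilirubin normal at baseline" and asks for a bilirubin rise that is "mainly conjugated fraction] without notable increase in ALP to" more than 2xULN.
- Section 6.3.2.2 uses multiples of baseline when AST, ALT or bilirubin is raised at the start.
- Table 14-6, for a combined rise, uses "ALT > 2 x baseline or > 300 U/L (whichever occurs first" when ALT is raised at baseline. For bilirubin it uses "TBL > 2 x ULN (or INR > 1.5", but in Gilbert's syndrome it asks for a doubling of direct bilirubin.

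**What else the SAP plans.** CTC shift tables from baseline to worst value, one laboratory parameter at a time; listings of all laboratory data (2.8.3); and listings of all baseline data (2.3).

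**The concern.** A patient with liver metastases whose ALT sits unchanged at 4xULN already satisfies the transaminase half of both rows. If bilirubin then passes 2xULN, perhaps because the metastases grow, the patient is counted. A patient with Gilbert's syndrome and stable TBL of 2.5xULN is counted as soon as ALT passes 3xULN. In the table, both look the same as a patient who started with normal tests and had both rise on treatment.

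The trial has no control arm to show how often this happens in patients with liver metastases. Hy's law counts are usually small and read closely, so one or two such patients can change how the row is understood. A reader of the table cannot tell how many counted patients belong to the normal-baseline group that the protocol's own trigger describes.

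**Working it through.** The SAP gives no figure to reproduce here. The check applies the written rules to three illustrative patients. Their values are assumptions chosen inside the entry limits.

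**Rules** (all values in xULN; b = baseline ALT or AST, t = baseline TBL)

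- SAP combined row: ALT or AST > 3 and TBL > 2.
- SAP Hy's law row: the same, plus ALP < 2 in the same sample.
- Protocol 6.3.2.2, all tests normal at baseline: ALT or AST > 3 and TBL > 2.
- Protocol 6.3.2.2, any test raised at baseline: ALT or AST above min(max(2b, 3), 8), and TBL above max(2t, 2).

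**Limits where the stable value already meets half of the SAP rule**

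- ALT/AST at b = 4: min(max(8, 3), 8) = 8. At b = 5: min(max(10, 3), 8) = 8. The SAP limit is 3.
- TBL at t = 2.5: max(5.0, 2) = 5.0. The SAP limit is 2.

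**Three patients**

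| Patient | ALT | TBL | ALP | SAP combined row | SAP Hy's law row | Protocol 6.3.2.2 |
|---|---|---|---|---|---|---|
| 1. Hepatic metastases, ALT stable | 4.0 to 4.0 | 0.8 to 2.2 | 1.5 | counted | counted | not met (ALT 4.0 is not above 8) |
| 2. Gilbert's syndrome, TBL stable | 0.8 to 3.5 | 2.5 to 2.5 | 1.0 | counted | counted | not met (TBL 2.5 is not above 5.0) |
| 3. Normal baseline, both rise | 0.8 to 4.0 | 0.8 to 2.2 | 1.5 | counted | counted | met |

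Patients 1 and 3 have identical on-treatment values and differ only at baseline.

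**Table 14-6 for the same patients.** Patient 1 fails the ALT part unless ALT exceeds 300 U/L. The laboratory ULN is not given. A stable 4xULN stays at or below 300 U/L for any ULN up to 300/4 = 75 U/L, and a stable 5xULN for any ULN up to 300/5 = 60 U/L. Patient 2 fails the combined rule provided direct bilirubin has not doubled, INR is at or below 1.5 and there are no liver symptoms.

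**Do the shift tables recover the split?** On CTC grades the cells are:

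| Patient | ALT shift | TBL shift |
|---|---|---|
| 1 | 2 to 2 | 0 to 2 |
| 2 | 0 to 2 | 2 to 2 |
| 3 | 0 to 2 | 0 to 2 |

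Each table covers one test, so its cells cannot be linked to the joint count. Bilirubin grade 2 runs from above 1.5 to 3.0xULN (protocol Table 6-3), so a baseline grade 2 does not isolate values above 2xULN.

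**When can each row be evaluated?** The partial chemistry panel holds ALT, AST and TBL; ALP and direct bilirubin are only in the full panel (Table 7-5). Table 7-1 schedules the full panel at screening, C2D1 and end of treatment, and the partial panel at C1D15 and on Day 1 of later cycles. After baseline, scheduled samples therefore support the combined row throughout, but the Hy's law row only at C2D1 and end of treatment. Unscheduled and work-up samples can add to this.

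**The case against.** **Absolute ULN limits are a proper sensitive screen, and the row says only potential.** This stands. A reader might infer that patients 1 and 2 are false positives to be removed, or that the SAP contradicts the protocol. The documents support neither. Each patient has a real rise in one test. The protocol rules cited govern follow-up and dosing, not tables, and Protocol 10.5.2.3 itself asks for worst post-baseline grades irrespective of baseline.

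**Few patients are involved.** This also stands. A reader might infer that every raised baseline is affected. It is not: a stable ALT of 2xULN or TBL of 1.5xULN never satisfies its half of the rule. Only ALT/AST above 3 and up to 5xULN, or TBL above 2xULN, does so.

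**The Novartis Liver Toxicity guidelines named in the SAP may handle baseline.** They are not among the documents, so this cannot be excluded. The point covers only the rows that the SAP writes out.

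**The information is already available.** In part. The listings allow case review, and the ALT and AST shift tables bound the number who started above 3xULN, since grade 2 begins there. Confirmed drug-induced liver injury is reported as an SAE (6.3.2.2). But none of these tells a reader of the summary table which counted patients started where.

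**Conclusion.** The point holds as a cheap improvement in presentation, at the level of something to consider. SAP 2.8.3 counts two combined liver rows without regard to baseline, criterion 10 admits patients who already meet one half, and no planned summary table separates them from patients who started normal.

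The number affected is unknown, because the documents give no baseline distribution, and probably small. A claim that the rows are inflated by any particular amount would go beyond the documents. No efficacy result, hypothesis test or stopping rule is touched; the effect is confined to how the safety table reads. For the Hy's law row it is narrower still, given how seldom ALP is scheduled. The conclusion assumes that the rows are programmed as written and that the guidelines outside the documents add no baseline split.

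**What to change.** Leave every ULN row unchanged and add to SAP 2.8.3, for example:

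> The combined ALT/AST and TBL row and the potential Hy's law row will be shown overall and by baseline status (baseline as in Section 2.1.1): (a) ALT, AST and TBL all at or below ULN; (b) any above ULN, but neither ALT/AST above 3xULN nor TBL above 2xULN; (c) ALT or AST above 3xULN, or TBL above 2xULN; (d) missing. Patients with known Gilbert's syndrome will be footnoted.

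Group (c) is the one that matters: a single group for any value above ULN would mix a patient starting at 1.1xULN with one starting at 4xULN. Group (c) shows who met half the rule at entry. It does not show that only the other test moved, so those cases still need reading in the listings.

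A count meeting protocol 6.3.2.2 may be shown alongside but must not replace the rows. For example, ALT going from 4 to 7.9xULN stays under that rule's limit of 8xULN, whatever bilirubin does.

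The cost is a short SAP addition and a few programming lines on data already collected. The downside is a few extra rows with small, often zero, counts. If the Core Phase tables are already final, a labelled supplementary table serves the same purpose.
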